5.3.3. Concomitant medications

Table 14 Other diabetic medication exposure definitions

Exposure	Definition	Details	Data source
Concomitant use of insulin at index date	Variable indicating the concomitant use of insulin with study drugs at index date, using data within the 180-day period prior to index date. ATC codes for insulins in Annex II. Evaluated at index using data within the 180-day period prior to index date.	Time-fixed Categorical: Yes No	UK: CPRD Sweden: SPDR Finland: FPR
Ever exposed to insulin	Variable indicating any use of insulin using data from 180 days prior to index date onwards. ATC codes for insulins in Annex II. Updating from 180 days prior to index date onwards.	Time-dependent Categorical: Yes No	UK: CPRD Sweden: SPDR Finland: FPR
Metformin exposure	Time updating current exposure status to metformin based on purchased amounts and daily defined or prescribed dose, using data from 180 days prior to index date onwards. ATC codes for metformin in Annex II. Updating from 180 days prior to index date onwards.	Time-dependent Categorical: Yes No	UK: CPRD Sweden: SPDR Finland: FPR
Ever exposed to metformin	Variable indicating any use of metformin using data from 180 days prior to index date onwards. ATC codes for metformin in Annex II. Updating from 180 days prior to index date onwards.	Time-dependent Categorical: Yes No	UK: CPRD Sweden: SPDR Finland: FPR
Ever exposed to GLP-1 drugs	Variable indicating any use of GLP-1 drugs using data from 180 days prior to index date onwards. ATC codes for GLP-1 drugs in Annex II. Updating from 180 days prior to index date onwards.	Time-dependent Categorical: Yes No	UK: CPRD Sweden: SPDR Finland: FPR

Proprietary confidential information © 2024 Boehringer Ingelheim International GmbH or one or more of its affiliated companies

Ever exposed to thiazolidinedi ones	Variable indicating any use of thiazolidinediones using data from 180 days prior to index date onwards.	Time-dependent Categorical: Yes No	UK: CPRD Sweden: SPDR Finland: FPR
	ATC codes for thiazolidinediones in Annex II.		
Updating from 180 days prior to index date onwards.			
Ever exposed to sulfonylureas	Variable indicating any use of sulfonylureas using data from 180 days prior to index date onwards.	Time-dependent Categorical: Yes No	UK: CPRD Sweden: SPDR Finland: FPR
	ATC codes for sulfonylureas in Annex II.		
Updating from 180 days prior to index date onwards.			
Ever exposed to other glucose lowering medication	Variable indicating any use of oral glucose lowering drugs other than the study drugs using data from 180 days prior to index date onwards.	Time-dependent Categorical: Yes No	UK: CPRD Sweden: SPDR Finland: FPR
	ATC codes for other glucose lowering drugs in Annex II.		
Updating from 180 days prior to index date onwards.			
Treatment complexity at index	Treatment complexity at index date is categorized by the number of drug classes in concomitant use including study drugs, using data from 180 days prior to index date onwards.	Time-fixed Categorical: Monotherapy Dual combination therapy Triple combination therapy or higher	UK: CPRD Sweden: SPDR Finland: FPR
	Evaluated at index using data from 180 days prior to index date onwards.		

Table 15 Other non-diabetic concomitant medication use variables

Variable	Definition	Details	Data source
Antihypertensive s/diuretics exposure at index date	Exposure status at index date of any antihypertensives/diuretics (including combinations) based on purchased amounts and daily defined dose using data within 180-day period prior to index date. ATC codes for antihypertensives/diuretics in Annex II. Evaluated at index date using data within 180-day period prior to index date.	Time-fixed Categorical: Yes No	UK: CPRD Sweden: SPDR Finland: FPR
Non-steroidal anti-inflammatory drugs (NSAIDs) exposure at index date	Exposure status at index date of any NSAID (including combinations) based on purchased amounts and daily defined dose using data within 180-day period prior to index date. ATC codes for NSAID in Annex II. Evaluated at index date using data within 180-day period prior to index date.	Time-fixed Categorical: Yes No	UK: CPRD Sweden: SPDR Finland: FPR
Oral steroids exposure at index date	Exposure status at index date of any oral steroid (including combinations) based on purchased amounts and daily defined dose using data within 180-day period prior to index date. ATC codes for oral steroids in Annex II. Evaluated at index date using data within 180-day period prior to index date.	Time-fixed Categorical: Yes No	UK: CPRD Sweden: SPDR Finland: FPR
Statins, fibrates exposure at index date	Exposure status at index date of any statin or fibrate (including combinations) based on purchased amounts and daily defined dose using data within 180-day period prior to index date. ATC codes for statins, fibrates in Annex II. Evaluated at index date using data within 180-day period prior to index date.	Time-fixed Categorical: Yes No	UK: CPRD Sweden: SPDR Finland: FPR

Proprietary confidential information © 2024 Boehringer Ingelheim International GmbH or one or more of its affiliated companies

Lipid modifying agents exposure at index date	Exposure status at index date of any lipid-modifying agent (including combinations) based on purchased amounts and daily defined dose using data within 180-day period prior to index date.	Time-fixed Categorical: Yes No	UK: CPRD Sweden: SPDR Finland: FPR
ATC codes for lipid modifying agent in Annex II.			
Evaluated at index date using data within 180-day period prior to index date.			
Zoledronic acid exposure at index date	Exposure status at index date of any zoledronic acid (including combinations) based on purchased amounts and daily defined dose using data within 180-day period prior to index date.	Time-fixed Categorical: Yes No	UK: CPRD Sweden: SPDR Finland: FPR
ATC codes for zoledronic acid in Annex II.			
Evaluated at index date using data within 180-day period prior to index date.			
Antibiotics exposure at index date	Exposure status at index date of any antibiotic (including combinations) based on purchased amounts, daily defined dose and dose per time estimation using data within 180-day period prior to index date.	Time-fixed Categorical: Yes No	UK: CPRD Sweden: SPDR Finland: FPR
ATC codes for antibiotic in Annex II.			
Evaluated at index date using data within 180-day period prior to index date.			

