Current exposure to study treatment (as-treated analysis)	Indicator of current use of empagliflozin, or a DPP-4 inhibitor, either alone or as a combination.	Time-dependent
Exposure to Empagliflozin (Intention-to-treat)	Drug purchased/prescribed at index date, which is one of empagliflozin, or a DPP-4 inhibitor.	Fixed at index date
Cumulative dosage of empagliflozin use	Time-dependent cumulative sum of drug consumption based on the daily defined dosage of empagliflozin since entry into the study cohort.	Time-dependent
Daily dosage of empagliflozin per use	The dosage of empagliflozin prescribed per daily use (10mg vs 25mg).	Time-dependent
Time since first dose of empagliflozin	Time-dependent cumulative sum of duration since the first use of (exposure to) empagliflozin.	Time-dependent
Treatment complexity	Monotherapy, dual combination therapy, or triple combination therapy (based on predefined groups).	Fixed at index date
Switch	Switch from the drug purchased/prescribed on index date to any other drug in the primary exposure.	Time-dependent
Concomitant use of insulin	Was empagliflozin an add-on to insulin (yes/no).	Fixed at index date
Concomitant use of metformin	Was empagliflozin an add-on to metformin (yes/no).	Fixed at index date
Concomitant use of metformin	Concomitant use of metformin either as fixed-dose combination or free combination.	Time-dependent
Ever used other oral glucose lowering medication	Use of other oral glucose lowering drugs based on predefined drug groups in the past.	Time-dependent
Ever used metformin	Was metformin ever used – taking value 'yes' as soon as one prescription with metformin is purchased.	Time-dependent

Exposure definition	Description	Time-dependent or Fixed at index date
Ever used sulphonylureas	Was sulphonylureas ever used – taking value ‘yes’ as soon as one prescription with sulphonylureas is purchased.	Time-dependent
Ever used thiazolidinediones	Was thiazolidinediones ever used – taking value ‘yes’ as soon as one prescription with thiazolidinediones is purchased.	Time-dependent
Ever used GLP-1	Was GLP-1 ever used – taking value ‘yes’ as soon as one prescription with GLP-1 is purchased.	Time-dependent
Ever used insulin	Was insulin ever used – taking value ‘yes’ as soon as one prescription with insulin is purchased.	Time-dependent

GLP=glucagon-like peptide

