8	13-APR-2022	6.7.2	The description of the Crude, base and fully adjusted models was aligned with the protocol. Additional criteria for selecting covariates for adjustment were introduced.	The incidence rates observed in the 5 th interim report suggest there will be few events for outcomes such as renal cancer. With few events, it will not be possible to build a model including all selected confounders. The chosen method limits the covariates of the model to confounders which are not balanced in the matched sample.

Proprietary confidential information © 2024 Boehringer Ingelheim International GmbH or one or more of its affiliated companies

9	13-APR-2022	Multiple	Pooled analysis of individual level data are replaced with aggregate level data meta-analyses. Pooled IRs will be estimated by pooling aggregate level data. Pooled HRs will be estimated using meta-analysis methods.	Individual level data from Finland and Sweden cannot be pooled together due to new regulations in the storage and use of individual level data in Sweden and Finland.
10	13-APR-2022	Multiple	Covariate selection criteria were added to mitigate the effect of missing data as well as potential Cox model convergence failures due to small number of events.	Observed incidence rates in interim report 5 suggests that there will be very few events observed for some outcomes such as renal cancer. In addition, stratified analyses that were to be carried out on pooled individual data will now be carried out at the single country level. It is therefore necessary to plan for possible convergence failure for some Cox proportional hazards models.

Proprietary confidential information © 2024 Boehringer Ingelheim International GmbH or one or more of its affiliated companies

12	13-APR-2022	Multiple	
Specified algorithms for inclusion and exclusion criteria
 
Redefined the AT and ITT exposure definitions as two time-fixed variables
 
Adjusted the definitions of time at risk, latency period and treatment discontinuation.
 
Specified algorithms for drug exposure definitions.
 
Removed stratification of metformin use from stratified analyses. (Analyses in study groups have covered subgroups by metformin use)
 
Changed some covariates from time-dependent to time-fixed
	Modifications made to clarify the expected analyses for programmers.

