4.2.3. BASELINE AND LOOK-BACK PERIOD

To characterize the empagliflozin and DPP-4 inhibitor cohorts at the time of study drug initiation, all information available during the look-back (pre-index) time period will be collected.

The look-back time period is defined as the time period ending on the day before the index date (Table 1). Since all cohort members are required by inclusion criteria to have at least 1 year of data before the index date (baseline period), the look-back period will include at least 365 days during which covariates can be evaluated. For some study participants, data on covariates might be available beyond 1 year prior to the index date; in these cases, all available information will be considered for covariate classification related to diabetes, diabetes medications, and concomitant chronic conditions. For concomitant medications for diseases other than diabetes, the look-back time period will be limited to 180 days prior to the index date.

Proprietary confidential information © 2024 Boehringer Ingelheim International GmbH or one or more of its affiliated companies

Table 1 Data sources with look-back periods and total data collection periods.

Data source	Data holder	Look-back period	Total data collection period
United Kingdom (UK)			
Clinical Practice Research Datalink, General practitioner OnLine Data (CPRD-GOLD)	Clinical Practice Research Datalink (CPRD)	1 st Jan 1987 – index date	1 st Jan 1987 – 31 st Dec 2021
Clinical Practice Research Datalink, Aurum (CPRD Aurum)	Clinical Practice Research Datalink (CPRD)	1 st Jan 1995 – index date	1 st Jan 1995 – 31 st Dec 2021
Hospital Episode Statistics (HES)	Clinical Practice Research Datalink (CPRD)	1 st Jan 1997 – index date	1 st Jan 1997 – 31 st Dec 2021
Sweden			
Swedish prescribed drug register (SPDR) ¹	National Board of Health and Welfare	1 st Jul 2005 – index date	1 st Jul 2005 – 31 st Dec 2020
National patient register (NPR), both inpatient ² and outpatient ³ registers	National Board of Health and Welfare	Inpatient: 1 st Jan 1997 – index date Outpatient: 1 st Jan 2001 – index date	Inpatient: 1 st Jan 1997 – 31 st Dec 2020 Outpatient: 1 st Jan 2001 – 31 st Dec 2020
Swedish cancer registry (SCR) ⁴	National Board of Health and Welfare	1 st Jan 1958 – index date	1 st Jan 1958 – 31 st Dec 2020
Cause of death register ⁵	National Board of Health and Welfare	Not applicable	1 st Jan 2014 – 31 st Dec 2020

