6.5. IMPLEMENTATION OF THE PROPENSITY SCORE MATCHING

6.5.1. Estimation of the propensity score

Propensity score model specification

The propensity score will be estimated using a binary logistic regression model. For all individuals, propensity scores for the comparison empagliflozin vs. DPP-4 inhibitors will be computed at the index date as the probability to receive empagliflozin, conditional on treatment and clinical history up to index date within each stratum.

The resulting propensity score model will be used to create two matched cohorts in each country:

- Matched full cohort, including patients initiating empagliflozin or a DPP-4 inhibitor at index date.
- Matched metformin-user only cohort, including patients using metformin in free or fixed dose combination with empagliflozin or a DPP-4 inhibitor at index date.

Variables considered for inclusion in the propensity score model

The following variables will be evaluated at index date and considered for inclusion in the propensity score model:

- Demographics and other baseline characteristics at index date Table 11.
- Diabetic complications Table 12 (status at index date).
- Non-diabetic concomitant disease Table 13 (status at index date).
- Diabetic concomitant medication use Table 14 (status at index date).
- Non-diabetic concomitant medication use Table 15 (status at index date).

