6.7.2. Comparative analysis

Hazard ratios (HRs) for the outcomes defined in Table 8 will be estimated for PS matched cohorts using Cox's PH model with time-varying covariates, if model pre-requisites are fulfilled. HRs will be presented along with 95% CIs. Proportional hazards assumptions for time-fixed exposure variables will be assessed for each model by plotting scaled Schoenfeld residuals.

The comparative analyses will be performed separately for the matched full cohort and matched metformin-user cohort.

Crude model

Crude HRs are calculated using a Cox PH model with as-treated exposure (as defined in Section 5.1.7) as the only included variable.

HRs estimated using the crude model will be presented along with 95% CIs. A table template for the result is given in Table 23. Analysis will be performed separately for each country.

Crude HRs with 95% CIs will be collected from all study countries to carry out meta-analyses as described in Section 6.7.3.2. Results will be reported as in Figure 8.

Base model

Based on the crude model, the base model will be further adjusted with the unbalanced covariates at index date (standard difference $\geq 10\%$) among the variables included in the propensity score model (Section 6.6). The inclusion of adjusting variables will be considered based on data availability as described in Section 10.

HRs estimated using the base model will be presented along with 95% CIs. A table template for the result is given in Table 24. Analysis will be performed separately for each country. HRs with 95% CIs estimated using base model will be collected from all study countries to carry out meta-analyses as described in Section 6.7.3.2. Results will be reported as in Figure 8.

Adjusted model

The base model will be further adjusted with selected time-dependent variables. The following time-dependent variables will be initially considered for inclusion (as detailed in Section 9) in the adjusted Cox's PH model:

- HbA1c value (as defined in Table 11)
- Kidney or genitourinary stones (as defined in Table 13)
- UTI or pyelonephritis (as defined in Table 13)
- Ever exposed to insulin (as defined in Table 14)
- Ever exposed to metformin (as defined in Table 14)

Proprietary confidential information © 2024 Boehringer Ingelheim International GmbH or one or more of its affiliated companies

- Ever exposed to other glucose lowering medication (as defined in Table 14)
- Ever exposed to GLP-1 drugs (as defined in Table 14)

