- Ever exposed to thiazolidinediones (as defined in Table 14)
- Ever exposed to sulfonylureas (as defined in Table 14)

HRs estimated using the adjusted model with time-dependent covariates will be presented along with 95% CIs. A table template for the result is given in Table 25. Analysis will be performed and model adjustment will be applied separately for each country.

Adjusted HRs with 95% CIs will be collected from all study countries to carry out meta-analyses as described in Section 6.7.3.2. Results will be reported as in Figure 8.

Handling of model convergence failure

For outcomes with a small number of events, convergence failure of multivariable Cox PH regression model may happen if there are no events for a particular combination of covariate values. Thus, a minimum of 5 outcome events per category of a variable is required for it to be included in the Cox model. In case of persisting model convergence failure while meeting this minimum requirement, the included covariates will be removed sequentially based on the rank of their PS standardised differences. The covariate with the smallest standardised difference will be removed iteratively until the model converges. In case of ties in selection, the choice is made randomly. The removed covariates will be reported along with the HR estimates.

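### SAP Table 14 starts all six 'Ever exposed' diabetes-drug variables 180 days before index, although SAP 4.2.3 and the protocol call for full history, so patients with only earlier use are coded 'No'

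*SAP*

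**What the plan says.** SAP 4.2.3 sets the look-back rule. Where a patient has more than one year of data, "all available information will be considered for covariate classification related to diabetes, diabetes medications, and concomitant chronic conditions". The shorter window is reserved for other drugs: "For concomitant medications for diseases other than diabetes, the look-back time period will be limited to 180 days prior to the index date". Protocol 8.2.4 has the same two sentences. Protocol section 8.3.1, Table 3, turns the thiazolidinedione 'ever used' variable to yes "as soon as one prescription with thiazolidinediones is purchased", and gives no start of ascertainment.

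SAP section 5.3.3, Table 14, does something else. Its thiazolidinedione row reads "Variable indicating any use of thiazolidinediones using data from 180 days prior to index date onwards". The rows for insulin, metformin, GLP-1 drugs, sulfonylureas and other glucose-lowering medication have the same start.

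The Table 14 variables feed two models. For the propensity score, SAP 6.5.1 says "The following variables will be evaluated at index date and considered for inclusion in the propensity score model" and lists Table 14 among them. For the adjusted Cox model, SAP 6.7.2 says "The following time-dependent variables will be initially considered for inclusion" and lists all six 'Ever exposed' variables by reference to Table 14. The change log (SAP section 3, item 12) records only "Specified algorithms for drug exposure definitions", with the general reason that the edits clarify the analyses for programmers.

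**The concern.** Programmers have two incompatible instructions for the same confounders. If they follow Table 14, a variable named 'ever' measures recent use before index plus any use afterwards. A patient who stopped a drug class more than 180 days before index and never resumed it is coded as never exposed.

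This matters most for thiazolidinediones. Protocol 8.1 mentions safety concerns about the class that include bladder cancer, which is a primary outcome here. Protocol Annex 4 marks the class for the propensity score and for adjustment as a potential confounder. Protocol 6.2 suggests that much of the use was early: with metformin, the class fell from 34% of UK second-line regimens in 2007 to 9.8% in 2010, the year in which rosiglitazone was suspended in the EU.

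If former use differed between the matched arms, the visible primary models would not control it and the post-matching diagnostics would not reveal it. Base-model covariates are chosen by standardized difference (SAP 6.6.2 and 6.7.2), so an imbalance that is not measured cannot trigger adjustment.

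**Working it through.** The plan states no figure for this point, so the check compares texts, with some date arithmetic and an illustrative bias calculation.

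**1. Definitions side by side**

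| Source | Diabetes-drug history used |
|---|---|
| SAP 4.2.3 and protocol 8.2.4 | All available pre-index data; 180 days for non-diabetes drugs only |
| Protocol Table 3 | 'Yes' from one prescription; for other oral drugs, use in the past |
| SAP Table 14 | Six of six 'Ever exposed' variables start 180 days before index |

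A patient whose last use of a class was more than 180 days before index, with none later, is 'Yes' under SAP 4.2.3 and 'No' under Table 14.

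**2. Other places in the SAP that do not fit Table 14**
- For patients without a recorded diagnosis, the Swedish and Finnish algorithms in SAP 4.2.4 accept a metformin prescription at any time before index as evidence of type 2 diabetes. Such a patient can enter because of past metformin and then be coded never exposed to it.
- At index, the 'ever' and 'concomitant' insulin variables draw on the same 180-day period, so they hardly differ.
- Balance Table 18 lists these classes only at index date. Table 17 has rows for use before index, but it describes the cohort before matching, and Table 14 does not define a window for those rows.

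**3. How much history is ignored**
- Every patient has at least 365 days of look-back. Ignored: 365 − 180 = 185 days, and 185/365 = 51%, plus everything earlier.
- Taking the register start dates in SAP Table 1, and index dates from 1 August 2014 to the end of study, 180 days is 3.2–5.4% of the longest possible history in the Swedish register, 1.8–2.4% in the Finnish, 1.4–1.8% in GOLD and 1.8–2.5% in Aurum. Individual histories may be shorter.
- The earliest window opens on 1 August 2014 − 180 days = 2 February 2014. From 31 December 2010 that is 1,129 days, or 3.1 years. No patient's window can reach rosiglitazone use before the 2010 suspension, although rosiglitazone combinations are in the thiazolidinedione code list (SAP Annex II).

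**4. Illustrative size**

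Let pE and pD be the proportions with uncaptured former use in the empagliflozin and DPP-4 arms, and h the hazard ratio of former use for the outcome. All three are assumed; the documents give none of them. The observed hazard ratio is multiplied by

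(1 + pE(h − 1)) / (1 + pD(h − 1))

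| pE | pD | h | Factor |
|---|---|---|---|
| equal to pD | any | any | 1 |
| 0.11 | 0.10 | 1.1 | 1.011/1.010 = 1.001 |
| 0.09 | 0.10 | 1.1 | 1.009/1.010 = 0.999 |
| 0.07 | 0.02 | 1.4 | 1.028/1.008 = 1.020 |
| 0 | 0.05 | 1.4 | 1/1.020 = 0.980 |
| 0.20 | 0.10 | 2.0 (extreme) | 1.2/1.1 = 1.091 |
| 0.10 | 0.20 | 2.0 (extreme) | 1.1/1.2 = 0.917 |

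For pD of 2–10%, a gap of 0–5 points either way and h of 1.1–1.4, the factor stays between 0.980 and 1.020. For scale, protocol Table 9 gives a minimum detectable hazard ratio of 1.47 for bladder cancer in the meta-analysis.

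**The case against.** The best defence is that protocol 8.3 leaves operational definitions to the analysis plan, that Table 14 is the specific definition, and that its consistent 180-day window looks deliberate. A short window also has merit: every patient has it in full, whereas all-history flags depend on look-back, and the prescription data start in 1987, 1994, 1995 or 2005 depending on the source. Most single-drug rows of protocol Table 3 do not say when ascertainment begins. The delegation argument fails because the SAP contradicts its own section 4.2.3, but the point about uneven history stands.

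Several limits on the consequences also stand:
- The 34% to 9.8% fall is UK data for metformin combinations only. Protocol Table 2 shows continuing thiazolidinedione use (9,849 UK patients in 2014–2015, 1,535 in Sweden in 2014, 4,565 in Finland in 2017), and use within 180 days of index or later is captured.
- Protocol 6.2 ties the rosiglitazone suspension to cardiovascular safety. It shows when use occurred, and is no evidence of a bladder cancer link for that drug.
- Treated-diabetes duration, time since diagnosis, complications, HbA1c and treatment complexity are propensity-score candidates, and matching is exact on metformin use at index. These cover treatment stage, but not former use by class.
- The variables are candidates. They can be dropped under the missing-data rule (SAP section 9) or, in the Cox model, under the five-events-per-category and convergence rules.
- The text of some sensitivity analyses is not visible, so the point applies to the propensity score and Cox models that can be read.
- The Table 18 gap follows from the definition and is not a second defect.

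**Conclusion.** The concern holds. SAP Table 14 conflicts with SAP 4.2.3 and protocol 8.2.4, most clearly for these six variables, and does not fit the plain meaning of 'ever used' in protocol Table 3. No reason is given for the window. Applied as written, it codes former-only users as never exposed wherever the variable is retained.

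The effect on the hazard ratio is of unknown size and sign, because the documents give neither the prevalence of former-only use nor its difference between arms. It is probably small: 0.980 to 1.020 under the moderate assumptions, about 0.92 or 1.09 under an extreme one, and none if the arms do not differ. The case for correction is that a confounder named in the protocol is measured differently from the stated rule, and that the planned diagnostics could not show whether this matters. It should be corrected before the analysis.

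**What to change.** In SAP Table 14, define the six 'Ever exposed' variables on all available prescription history before index, updating afterwards, as SAP 4.2.3 states. Keep the 180-day window for concomitant insulin at index, current metformin exposure and treatment complexity. Add pre-index 'ever' rows to balance Table 18, and use the same definition for the prior-use rows in Tables 17 and 37. Keep duration of look-back (Table 11) in the propensity score to deal with uneven history.

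If 180 days is intended, rename the variables, give the reason and amend 4.2.3.

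No new data are needed. SAP Table 1 already covers prescriptions from July 2005 (Sweden), 1994 (Finland), and 1987 and 1995 (GOLD and Aurum), and full prescription history is already used for the prior-use exclusion and for treated-diabetes duration. The cost is a text edit and extra table rows. If the propensity score is already programmed, its estimation, the matching and the downstream models must be rerun in three countries, including in the Findata environment. The drawback is that all-history flags detect past use unevenly across patients and countries.
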